### Missing date convention

Please note that for below AE missing date imputation, all infusion dates or treatment dates refer to those in the extension study.

**Partial AE start dates:** If an AE start date is completely missing, then no imputation is implemented. AEs with completely missing start dates will be treated as treatment emergent. If the year of an AE start date is missing but the month is available, then the date will be imputed as the start date of the first study drug infusion + 1.

If the year is not missing and the month is missing, then date will be imputed as follows:

- If the AE year is less than the year the study drug infusion was administered, then July 1st of the year will be used.
- If the AE year is equal to the year the study drug infusion was administered, then the start date will be imputed as the start date of the first study drug infusion + 1.
- If the AE year is greater than the year the study drug infusion was administered, then the Jan 1st of the year will be used.

If the year is available and the month is non-missing, then the following rules will be applied relative to the month that study drug treatment was given:

- If the month in which the AE started is less than the month that the study drug infusion was administered, then:
  - If the AE year is less than or equal to the year the study drug infusion was administered, then the 15th day of the month will be used.
  - If the AE year is greater than the year the study drug infusion was administered, then the maximum of the first day of the month and the treatment start date + 1 will be used.
- If the month in which the AE started is equal to the month that the study drug infusion was administered, then:
  - If the AE year is less than the year the study drug infusion was administered, then the 15th day of the month will be used.
  - If the AE year is greater than or equal to the year the study drug infusion was administered, then the maximum of the first day of the month and the treatment start date + 1 will be used.
- If the month in which the AE started is greater than the month that the study drug infusion was administered, then:
  - If the AE year is less than the year the study drug infusion was administered, then the 15th day of the month will be used.
  - If the AE year is greater than or equal to the year the study drug infusion was administered, then the maximum of the first day of the month and the treatment start date + 1 will be used.

In case that the AE end date was completed, the AE start date imputed as above was after the AE end date, the AE start date was re-imputed using the AE end date.

**Partial AE end dates:** There is no STL convention to impute partial AE end date. Partial AE end date was imputed using (a) the last date of the month if only the day of AE end date is missing, (b) December 31 if only the year of AE end date is present. If a patient dies and the imputed end date is after the date of death, the date of death was imputed as the AE end date. When a patient dies, the end date for ongoing AEs was imputed using the date of death.

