Adverse events (D)	X	X	X	X	X	X	X	X	X	Any AEs that occur after Visit 8 but prior to first dose of Extension study (Visit 9) will be collected on the AE (e)CRF
Vital signs (D)	X		X			X			X	Pulse rate and blood pressure only
Physical examination (S)	X		X			X			X	Including an oral examination for exposed bone
Tanner staging (D), if applicable	X								X	
Weight (D)	X		X			X			X	
Pain assessment	X		X		X	X		X	X	Pain is assessed using Faces Pain Scale-Revised (FPS-R)
Central laboratory test (hematology, biochemistry including urinalysis)	X		X	X		X	X		X	All patients will have limited blood chemistry assessments, GFR and urinalysis performed at

	Final visit of Core study		Infusion visit		Tele-phone	Infusion visit		Tele-phone		Notes
Visit	8	8A	9	10	11	12	13	14	15/EOS and TD and/or PSW	Visit 8 is the Core study completion visit. Visit 8A lists the additional assessments which need to be completed for the Extension study. Visits 8 and 8A assessments must be completed on the same day. Visits 8, 8A, and 9 can occur on the same day
Months relative to the Core study (after Visit 9 - Baseline of Extension study)			up to 10 months after V5 (Core study)	10 days after V9	15 (3 months after V9)	18 (6 months after V9)	10 days after V12	21 (9 months after V9)	24 (12 months after V9)	
										Visit 10 and Visit 13
Serum creatinine (local lab)			X							For exclusion purposes
Ionized calcium (local lab)			X							Measured pre-dose, (local lab) prior to first infusion of Extension study
Bio-markers (Serum P1NP, NTX, BSAP, Trap-5b)	X		X			X			X	Not required at Visit 9 if it occurs within 30 days of Visit 8
Serum 25 hydroxy vitamin D	X		X						X	
Pregnancy Test	X		X		[X]	X			X	To be performed for females with childbearing potential only [Only for sites where additional safeguards are required: Supervised urine pregnancy test]
i.v. drug administration (zoledronic acid)			X			X				
Dispense calcium and vitamin D, if required		X	X			X				
DXA measurements (lumbar spine, total body and distal femur)	X		X			X			X	Not required if obtained 3 months prior to Visit 9
X-ray	X								X	Lateral thoraco-lumbar spine and postero-anterior left hand/wrist
Study completion	X								X	

S = Source data, D = Database, TD = study treatment discontinuation, PSW = premature patient withdrawal

Table 6-2 Group 2 Assessment schedule

	Screening Visit	Infusion Visit ¹		Tele- phone	Infusion Visit		Tele- phone		Notes

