## Adverse events

An adverse event (AE) is any untoward medical occurrence in a subject or clinical investigation subject after starting the study drug even if the event is not considered to be related to study drug. Treatment-emergent adverse events will be defined as adverse events that were absent prior to the first infusion in the extension study and occurred after the first infusion during extension study or that were present prior to the first infusion in the extension study and occurred at increased severity after the first infusion during extension study. Summarization will be based on treatment-emergent adverse events.

Adverse events will be coded using the Medical dictionary for regulatory activities (MedDRA). The number and percentage of patients who report adverse events will be summarized by treatment according to the primary system organ class and preferred term. If a patient reports more than one adverse event within the same primary system organ class (preferred term), the patient will be counted only once with the greatest severity at the system organ class (preferred term) level. Serious adverse events and selected adverse events will be presented by core treatment group code. Listing of these events will be provided.

Adverse event tables will be sorted alphabetically by system organ class and then according to decreasing frequency of preferred term in the zoledronic acid group. If only system organ classes or preferred terms are presented, these will be sorted according to the decreasing frequency in the zoledronic acid group.

The following sets of adverse events will be summarized:

- All adverse events (by primary system organ class and preferred term)
- Adverse events suspected to be related to study drug (by primary system organ class and preferred term)
- Adverse events that occurred after first infusion in the extension study and before second infusion in the extension study (by primary system organ class and preferred term)
- All adverse events (by primary system organ class, preferred term and maximum severity)

- All adverse events (by underlying disease group, primary system organ class and preferred term)
- Adverse events that result in death (by primary system organ class and preferred term)
- Serious adverse events (by primary system organ class and preferred term)
- Adverse events causing permanent discontinuation of study drug (by primary system organ class and preferred term)

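### Two adverse-event start-date rules override recorded data: undated starts count as treatment-emergent even if the event ended before dosing, and a known month without a year becomes Day 2

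*SAP*

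**What the plan says.** The rules are in the SAP, Safety evaluation, under the Missing date convention that follows the Adverse events section. All infusion dates there are those of the Extension.

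- Start wholly missing: "If an AE start date is completely missing, then no imputation is implemented". The next sentence reads "AEs with completely missing start dates will be treated as treatment emergent".
- Month recorded, year missing: the rule for a year that is "missing but the month is available, then the date will be imputed as the start date of the first study drug infusion + 1". Under the SAP's Study day rule this is Extension Day 2.
- Safeguard: "In case that the AE end date was completed, the AE start date imputed as above was after the AE end date", the start is set to the end date. It speaks only of a start that has been imputed.
- Partial end dates: the next paragraph fills them with the last day of the month, or with 31 December if only the year is known.

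The SAP's Adverse events section defines an event as treatment-emergent if it first occurs, or worsens, after the first Extension infusion. Among the planned tables is "Adverse events that occurred after first infusion in the extension study and before second infusion in the extension study". Times from the first Extension infusion to the first renal and first hypocalcaemia event are also planned, with Cox models.

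Protocol Table 6-1 (Group 1) shows that pre-dose events are in the data: "Any AEs that occur after Visit 8 but prior to first dose of Extension study (Visit 9) will be collected on the AE (e)CRF". Protocol Section 3.1 allows Visit 9 up to 4 months after Visit 8.

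**The concern.** An imputation rule should fill in what is unknown and leave alone what is known. These two rules do not.

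In the first, a recorded end date can prove that the event was over before dosing, yet the event is still counted as arising on treatment. In the second, a recorded month is thrown away even where it settles the date.

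Safety is the primary objective of this study. The first rule can add pre-dose events to the treatment-emergent tables. The second can put a late event into the table for the interval between the two infusions, and can place a renal or hypocalcaemia event on Day 2. For hypocalcaemia, the SAP takes the earlier of the adverse event and the low central calcium value, so a false Day 2 date would also displace a correctly dated laboratory value.

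**Working it through.** The plan gives no figure to reproduce, so the check is to apply the rules as written. The examples use a first infusion on 15 March 2016 (Day 1) and a second six months later, on 15 September 2016 (Day 185).

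**1. Event over before dosing, end date recorded as 1 February 2016**

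| Start recorded | Imputed start | Safeguard | Result |
|---|---|---|---|
| nothing | none | has no imputed start to act on | treatment-emergent |
| January, no year | 16 Mar 2016 | resets to 1 Feb 2016 | not treatment-emergent |
| 2016 only | 16 Mar 2016 | resets to 1 Feb 2016 | not treatment-emergent |

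The end date is the same in all three rows, and only the wholly undated start gives the wrong answer. I then applied the rules to every infusion date in 2017, with events in the 122 days (4 months) before infusion. Assumptions: event days are uniform and events last 5 days. With a complete end date, 100% of wholly undated events are counted as treatment-emergent, against 0% for each partial pattern (month only, year only, month and year).

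**2. Month known, year missing: October**

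On the nominal schedule, the collection window runs at its widest from 15 November 2015 (Visit 8, 4 months earlier) to 15 March 2017 (Visit 15). It holds one October, that of 2016.

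- 1 October 2016 is 200 days after infusion, so Day 201; 31 October is Day 231. Both are after the second infusion.
- The SAP rule gives 16 March 2016, Day 2, which falls between the infusions.
- A complete end date of 20 October 2016 (Day 220) does not help. The imputed start is not after it, so there is no reset and the event appears to run from Day 2 to Day 220.

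Over all 2017 infusion dates, the imputed month differs from the recorded month for 91.4% of on-study event days. The exception is the infusion month itself.

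**3. How often the month alone settles the year**

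Share of event days between Visit 8 and 365 days after Visit 9 for which the month occurs in one year only:

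| Gap from Visit 8 to Visit 9 | Year settled |
|---|---|
| 0 days | 91.4% |
| 30 days | 76.9% |
| 61 days | 64.1% |
| 122 days | 43.6% |

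Using the month therefore recovers much of the lost information, but a tie rule is needed.

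**4. Reach of the safeguard**

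Take an infusion on 20 October 2016, a start recorded as 2016 and an end recorded as August 2016. The imputed start is 21 October and the imputed end is 31 August. If the safeguard needs a fully recorded end date, the event starts after it ends and is treatment-emergent. If it also runs on the filled-in end date, the start becomes 31 August and the event is not treatment-emergent. The text allows both readings. On the narrow reading, where the partial end lies in a month wholly before infusion, the imputed start falls after the imputed end for 100% of month-only starts, 80.3% of year-only starts and 0% of month-and-year starts.

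**The case against.** Four points can be made for the plan.

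- **Counting an undated event as treatment-emergent is a cautious default in a safety study.** This stands where no end date contradicts it, and the default should be kept there.
- **Such records should be rare.** Protocol Section 7.1 asks for start and end dates for every event, Section 8.2 has automatic entry checks, and Section 8.3 has queries before lock. This stands as an argument about frequency. It does not make the rules correct for the records that remain.
- **The safeguard already prevents pre-dose events from being counted.** It does so for partial starts with a complete end date. A reader might infer that any event that ended before dosing becomes treatment-emergent; the 0% results above show that this is too broad.
- **A day-missing event in the month of the second infusion has to go somewhere.** A reader might infer a further error because September 2016 becomes 1 September, before a 15 September infusion. That date agrees with what was recorded. Choosing the other side would push true 1-14 September events past the infusion. This is a convention, and it is not part of this point.

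A reader might also infer that each misfiled event shifts an incidence rate by a fixed amount. The SAP counts a patient once per preferred term and once per system organ class, so an extra event changes nothing for a child already counted in that category. A late event moved to Day 2 is treatment-emergent either way, so only its timing changes. An event counted both as medical history and as treatment-emergent is possible, but not shown, because the SAP does not say how undated events enter the medical-history table.

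**Conclusion.** The point holds for two rules. A wholly missing start makes an event treatment-emergent even when its recorded end precedes the first Extension infusion, which contradicts the SAP's definition. A known month with a missing year is replaced by Day 2 unless a complete earlier end date resets it. Whether the safeguard covers imputed end dates is an ambiguity to settle, not a demonstrated error.

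The effect on the safety tables cannot be sized, because the documents give no count of partial dates and the number may be small. The percentages above apply within each missing-date pattern and rest on the uniform-day and 5-day assumptions and on nominal visit dates. The documents do not show that the overall safety conclusion, or the comparison between Core treatment groups, would change, or in which direction.

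**What to change.** Amend the SAP's adverse-event date convention before database lock:

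1. **Test the end date first.** If it is before the first Extension infusion, whether complete or imputed by the SAP's own end-date rule, the event is not treatment-emergent, whatever is known of the start. Otherwise keep the treatment-emergent default. Because the SAP fills partial ends with the latest possible day, this test removes no event that could have continued past the infusion.
2. **Month known, year missing:** use that month within Visit 8 to Visit 15. If two occurrences are possible, take the one on or after the first infusion (for the infusion month itself, the earlier). Then apply the existing day-missing rule. In the October example this gives 1 October 2016, Day 201.
3. **State that the start-after-end reset also applies to imputed end dates.**

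The cost is a few sentences of SAP text and a few lines of derivation code, with no new data. A listing of all adverse events with imputed or missing start dates would also show how many records the rules touch.

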### **Adverse events associated with change in renal function**

Adverse events associated with change in renal function are defined based on predefined search list which describe a clinically significant change in renal function. A search of the clinical trial database will occur based on this pre-specified list of MedDRA preferred terms. These adverse events will be summarized by preferred term. In addition, the event rate will be summarized. The hazard ratio, 95% CI and p-value based on a Cox proportional hazards model with core treatment and underlying condition treated with glucocorticoids (stratification factor) as explanatory variables will be presented. Meanwhile, to aid in the assessment that the treatment differences are not inconsistent across the strata, the treatment-by-stratification interaction term will be added to the model described above. P-value for the interaction term will be reported. If a patient experiences an adverse event associated with change in renal function, the event time is defined as the earliest of all events if there are

multiple. Otherwise, a patient is considered censored at the last contact date. Kaplan-Meier estimates will be plotted over time if at least 10% of overall population has experienced the event.

Patient listings will be provided for all adverse events associated with clinically significant change in renal function.

### **Hypocalcemia adverse events and laboratory events**

Hypocalcemia adverse events will be searched based on preferred term and summarized. Patients with reported laboratory measurements associated with a signal of hypocalcemia will be summarized by visit. Lab hypocalcemia (low serum calcium levels) is present if the value of serum calcium from central lab is less than the lower limit of normal range provided by the central lab.

The number and percentage of patients who met these criteria will be summarized by core treatment group and overall.

The hazard ratio, 95% CI and p-value based on a Cox proportional hazards model with core treatment and underlying condition treated with glucocorticoids (stratification factor) as explanatory variables will be presented. Meanwhile, to aid in the assessment that the treatment differences are not inconsistent across the strata, the treatment-by-stratification interaction term will be added to the model described above. P-value for the interaction term will be reported. If a patient experiences a hypocalcemia and low calcium value based on the central lab, the event time is defined as the earlier of these events. Otherwise, a patient is considered censored at the last contact date. Kaplan-Meier estimates will be plotted over time if at least 10% of overall population has experienced the event.

Patient listings will be provided for all adverse events associated with hypocalcemia.

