7.1 Adverse Events

An adverse event (AE) is any untoward medical occurrence (e.g., any unfavorable and unintended sign [including abnormal laboratory findings], symptom, or disease) in a patient or clinical investigation subject occurring after starting the study drug even if the event is not considered to be related to study drug. Therefore, an AE may or may not be temporally or causally associated with the use of a medicinal (investigational) product.

In addition, all reports of intentional misuse and abuse of the product are also considered an adverse event irrespective if a clinical event has occurred.

Group 1: all AEs following completion of the Core study (Visit 8) will be recorded in the eCRF of this extension study.

Group 2: due to the long screening period (at least 4 weeks), although SAEs are collected from signing the informed consent, the AE page of the eCRF is only completed from the first day of study drug; any events that occur prior to receiving study treatment, should be recorded in the eCRF as Medical History.

The occurrence of adverse events should be sought by non-directive questioning of the patient at each visit during the study. Adverse events also may be detected when they are volunteered by the patient during or between visits or through physical examination, laboratory test, or other assessments.

Abnormal laboratory values or test results constitute adverse events only if they fulfill at least one of the following criteria:

- they induce clinical signs or symptoms,
- they are considered clinically significant,
- they require therapy.

Clinically significant abnormal laboratory values or test results must be identified through a review of values outside of normal ranges/clinically notable ranges, significant changes from baseline or the previous visit, or values which are considered to be non-typical in patient with underlying disease. Investigators have the responsibility for managing the safety of individual patients and identifying adverse events. Alert ranges for laboratory and other test abnormalities are included in [Appendix 1](#).

Adverse events must be recorded on the Adverse Events CRF under the signs, symptoms or diagnosis associated with them, accompanied by the following information:

- the severity grade
 - mild: usually transient in nature and generally not interfering with normal activities
 - moderate: sufficiently discomforting to interfere with normal activities
 - severe: prevents normal activities.

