- Adverse events causing concomitant medication taken (by primary system organ class and preferred term)
- Adverse events associated with a change in renal function (by preferred term). Time from first infusion in the extension study to first adverse event associated with a change in renal function will be presented separately.

- █ [REDACTED]
- Hypocalcemia adverse events (by preferred term). Time from first infusion in the extension study to first hypocalcemia occurrence based on AE and central lab calcium will be presented separately.

Incidence of risk as defined in the case retrieval strategy, during the study period, will be summarized by core treatment group, and MedDRA levels. Relative risk of zoledronic acid group vs. placebo (core treatment A vs. core treatment B) will be presented along with corresponding 95% confidence intervals using the Mantel-Haenszel test.

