In addition, summary tables will be presented based on both baselines for the incidence rates of newly occurring clinically notable laboratory abnormalities, where patients will be counted if they have normal or missing baseline value and with at least one post-baseline assessment satisfying the clinically notable criteria. Incidence rates of newly occurring hypocalcemia (based on central lab) by visit will be summarized similarly for patients who have normal or missing baseline level of serum calcium and clinically notable abnormal serum calcium level at each scheduled post-baseline visit. The definition of clinically notable laboratory abnormalities can be found in Appendix section "Clinically notable laboratory values and vital signs" in the protocol.

Furthermore, summary tables will be provided for the number and percentage of patients with liver enzyme abnormalities by each study visit and with at least one post-baseline assessment satisfying the liver enzyme abnormalities compared against both baselines.

Listings of all laboratory parameter measurements will be displayed. The abnormal value will be flagged, e.g., L/H for a value being below/above normal range, and the lower and upper limit of normal values will be presented as well. Central lab calcium values will also be listed for patients with at least one post-baseline laboratory signal of hypocalcemia and the below normal serum calcium results will be flagged as L.

For each numerical laboratory parameter, the number of decimal places to be used for laboratory values should be the same as that for the normal range. For continuous variables recorded as *<lower limit>*, these will be imputed as being half of the lower limit.

All laboratory parameters will be expressed using SI units.

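### Read literally, the SAP's hypocalcaemia time-to-event rule needs both an adverse event and a low central calcium, so patients with only one of them are censored.

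*SAP*

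**What the plan says.** The rule is in the SAP section *Hypocalcemia adverse events and laboratory events*. Laboratory hypocalcaemia is defined there on its own, with no AE required: "Lab hypocalcemia (low serum calcium levels) is present if the value of serum calcium from central lab is less than the lower limit" of normal. The event rule for the Cox model follows: "If a patient experiences a hypocalcemia and low calcium value based on the central lab, the event time is defined as the earlier" of the two. The next sentence is: "Otherwise, a patient is considered censored at the last contact date". The same section adds a p-value for the interaction of core treatment with underlying condition, and a conditional plot: "Kaplan-Meier estimates will be plotted over time if at least 10% of overall population has experienced the event".

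The SAP section *Adverse events* describes the same output in its list of summaries: "Time from first infusion in the extension study to first hypocalcemia occurrence based on AE and central lab calcium will be presented separately".

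Protocol 7.1 decides when a laboratory value also becomes an AE: "Abnormal laboratory values or test results constitute adverse events only if they fulfill at least one of the following criteria". The criteria are that it causes signs or symptoms, is judged clinically significant, or needs therapy.

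**The concern.** The event sentence joins its two components with *and*, and the censoring sentence sends everyone else to last contact. I take the unqualified first component to be the hypocalcaemia AE, as the list of AE outputs implies. A programmer who follows the text would then count as event-free any patient with a low central calcium and no AE, and any patient with a hypocalcaemia AE and no low central value.

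Both types can occur in this trial:

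- **Laboratory only.** Under protocol 7.1 a low calcium is not automatically an AE, and protocol 5.1.2 says that post-infusion hypocalcaemia is transient and only rarely symptomatic.
- **AE only.** Local ionized calcium is measured before the first infusion (protocol 6.5.4.2). The first scheduled central calcium after dosing is at Visit 10, 10 days later (Tables 6-1 and 6-2, Appendix 7). A symptomatic episode in the first days could resolve before that sample.

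Safety is the primary objective, and hypocalcaemia is one of the few safety topics given its own Cox model. Two programmers could code this sentence differently and report different hazard ratios.

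**Working it through.** The plan states no event count, rate or power for this endpoint, so there is no figure to reproduce. The check has two parts: the logic of the rule, and an illustration with assumed rates.

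**1. Logic of the rule**

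| Hypocalcaemia AE | Low central calcium | As written (*and*) | Either source (*or*) |
|---|---|---|---|
| yes | yes | event, earlier date | event, earlier date |
| no | yes | censored | event |
| yes | no | censored | event |
| no | no | censored | censored |

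One of four patient types is an event as written; three of four are under *or*. The literal rule also has an internal oddity. A two-part condition is met only on the later date, yet the event is dated at the earlier one.

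The renal rule has no such problem because it draws on AEs alone: "If a patient experiences an adverse event associated with change in renal function, the event time is defined as the earliest of all events".

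**2. Illustration**

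Inputs:

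- N = 100. Protocol 9.6 gives about 100 for Groups 1 and 2 together. The SAP analyses Core completers only, and their number is not stated, so N = 100 is an upper-side assumption.
- p = proportion with a low central calcium: 5-20% (assumed).
- q = proportion of those who also have an AE: 10-50% (assumed).
- a = proportion of patients with normal calcium who have an AE: 0 or 3% (assumed).

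Formulas:

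- expected events under *and* = N·p·q
- expected events under *or* = N·[p + (1 − p)·a]
- laboratory-only patients censored under *and* = N·p·(1 − q)

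Results:

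- *And*: from 100 × 0.05 × 0.10 = 0.5 to 100 × 0.20 × 0.50 = 10.
- *Or*, a = 0: from 100 × 0.05 = 5 to 100 × 0.20 = 20.
- *Or*, a = 3%: from 100 × (0.05 + 0.95 × 0.03) = 7.85 to 100 × (0.20 + 0.80 × 0.03) = 22.4.
- Laboratory-only patients censored: from 100 × 0.05 × 0.50 = 2.5 to 100 × 0.20 × 0.90 = 18.

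With a = 0 the ratio of *or* to *and* is p/(p·q) = 1/q, which is 10 at q = 10% and 2 at q = 50%. It depends only on the assumed overlap.

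**3. Kaplan-Meier trigger**

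With N = 100 the plot needs at least 10 events. The binomial probability of 10 or more, with a = 0, is:

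| p | q | *and* | *or* |
|---|---|---|---|
| 5% | 25% | below 0.0001 | 0.028 |
| 10% | 25% | 0.0002 | 0.55 |
| 15% | 25% | 0.004 | 0.945 |
| 20% | 50% | 0.55 | 0.998 |

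At the low end the plot is unlikely under either reading. In the middle of the range the reading largely decides whether it is drawn.

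**The case against.** The strongest reply is that *either source* was plainly meant. The list of AE outputs speaks of a first occurrence drawn from two sources, which reads naturally as a composite. Dating the event at the earlier component makes full sense only under *or*. The renal rule likewise takes the first qualifying event. This is persuasive about intent, and a reader should not infer that the sponsor chose a both-required endpoint. But the list of outputs also says *and*, and nothing in it overrides the censoring sentence.

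The second reply is that little is lost, and this largely stands. Laboratory-only cases remain in the by-visit counts, the shift tables and the calcium listings, and also here: "Incidence rates of newly occurring hypocalcemia (based on central lab) by visit will be summarized similarly". AE-only cases remain in the AE tables. Both documents describe the safety analysis as descriptive, and protocol 9.4.1 treats any test as exploratory. A reader might infer that hypocalcaemia would go unreported; the documents do not support that.

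A reader might also infer that most low calcium values would have no AE. No rate is given, and Table 13-1 lists any out-of-range calcium under its criteria for clinically significant change, which could raise the overlap. Significance is still an investigator's judgement under protocol 7.1, so laboratory-only cases are possible but their share is unknown.

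The DMC concern recorded in the Amendment 3 rationale was about transient symptomatic hypocalcaemia after the first infusion. It does not bear on laboratory-only cases. Symptomatic episodes meet the AE criteria and stay in the AE tables, although the literal rule would censor one that had no low central value.

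**Conclusion.** The point holds as a wording defect in an operative rule. As written, the SAP gives an event only to patients with both components and censors both discordant types. The intent was probably either source, but the text does not say so.

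The effect is confined to the hazard ratio with its confidence interval and p-value, the interaction test, and the Kaplan-Meier plot with its trigger. Its direction is certain: *and* can never give more events than *or*. Its size is not known. The ranges above (0.5-10 against 5-20 expected events) rest wholly on the assumed rates and on N = 100, and no single multiple should be quoted as the undercount. At the low end of the *and* range, a Cox model with treatment, underlying condition and their interaction would have almost no events to work with. The correction should be made before programming, but no safety conclusion in the plan hangs on this hazard ratio alone.

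**What to change.** Replace the event and censoring sentences in the SAP's hypocalcaemia section with: *If a patient has a hypocalcaemia AE or a post-infusion central laboratory calcium below the lower limit of normal, the event time is the earlier of the two; patients with neither are censored at the last contact date.*

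In the SAP section *Adverse events*, change the description of the time-to-event output to match, with *or* between the two sources.

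The cost is two edited SAP sentences and a matching line in the programming specification. No new data, visits or protocol amendment are needed. Separate component tables are not essential, because the planned AE and laboratory summaries already show each source. If both components were in fact intended, the SAP should say so explicitly, give the reason, and date the event when the second component occurs.
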